8.5.2. Follow-up of Adverse Events and Serious Adverse Events

AEs, including pregnancy, will be followed by the investigator as specified in Section 10.4, Adverse Events: Definitions and Procedures for Recording, Evaluating, Follow-up, and Reporting.

8.5.3. Regulatory Reporting Requirements for Serious Adverse Events

The sponsor assumes responsibility for appropriate reporting of AEs to the regulatory authorities. The sponsor will also report to the investigator (and the head of the investigational institute where required) all suspected unexpected serious adverse reactions (SUSARs). The investigator (or sponsor where required) must report SUSARs to the appropriate Independent Ethics Committee/Institutional Review Board (IEC/IRB) that approved the protocol unless otherwise required and documented by the IEC/IRB. A SUSAR will be reported to regulatory authorities unblinded. Participating investigators and IEC/IRB will receive a blinded SUSAR summary, unless otherwise specified.

8.5.4. Pregnancy

All initial reports of pregnancy in female participants or partners of male participants must be reported to the sponsor by the study-site personnel within 24 hours of their knowledge of the

^a This section has been amended by amendment INT-3.

event using the appropriate pregnancy notification form. Abnormal pregnancy outcomes (eg, spontaneous abortion, fetal death, stillbirth, congenital anomalies, ectopic pregnancy) are considered serious AEs and must be reported using the Serious Adverse Event Form. Any participant who becomes pregnant during the study must be promptly withdrawn from the study and discontinue further study medication.

Follow-up information regarding the outcome of the pregnancy and any postnatal sequelae in the infant will be required.

8.6. Treatment of Overdose

For this study, any dose of JNJ-67953964 greater than 4 capsules within a 24-hour time period will be considered an overdose. The sponsor does not recommend specific intervention for an overdose.

In the event of an overdose, the investigator or treating physician should:

- Contact the Medical Monitor immediately.
- Closely monitor the participant for AE/SAE and laboratory abnormalities until JNJ-67953964 can no longer be detected systemically (at least 2 days).
- Obtain a plasma sample for PK analysis within 2 days from the date of the last dose of study medication if requested by the Medical Monitor (determined on a case-by-case basis).
- Document the quantity of the excess dose as well as the duration of the overdosing in the CRF.

Decisions regarding dose interruptions or modifications will be made by the investigator in consultation with the Medical Monitor based on the clinical evaluation of the participant.

8.7. Pharmacokinetics

Plasma samples will be analyzed to determine concentrations of JNJ-67953964 using a validated, specific and sensitive liquid chromatography-mass spectrometry/ mass spectrometry (LC-MS/MS) method. If required, some plasma samples may be analyzed to document the presence of circulating metabolites or to determine protein binding using a qualified research method. In addition, some samples may be used to measure plasma concentrations of the SSRI/SNRI used by the subject.

Venous blood samples of 6 mL will be collected for determination of JNJ-67953964 plasma concentrations when required specified in the TES. A PK blood sample will be collected at the same time as the blood samples for biomarkers when indicated in the TES.

The exact dates and times of blood sampling must be recorded in the laboratory requisition form.

Data will be listed for all subjects with available plasma concentrations per treatment and study day. All concentrations below the limit of quantification (LOQ) or missing data will be labeled as such in the concentration data listings. Concentrations below the LOQ will be treated as zero in the summary statistics.

8.8. Genetics

Blood samples (6 mL) will be collected to allow for the identification of pharmacogenomic factors that may influence the PK, PD, safety and/or tolerability of JNJ-67953964, and to identify genetic and epigenetic factors associated with neuropsychiatric/neurodegenerative disorders. They may also be used to develop tests/assays related to JNJ-67953964 or neuropsychiatric/neurodegenerative disorders.

Pharmacogenomic research may consist of the analysis of one or more candidate genes or of the analysis of (epi)genetic markers throughout the genome or analysis of the entire genome (as appropriate) in relation to JNJ-67953964 or neuropsychiatric/neurodegenerative disorders. All pharmacogenomic data obtained during this study may be included in ongoing cross-study analyses to investigate the relationship between depression severity and phenotypes and biomarkers. Participation in the genetic/pharmacogenomic part of this study is mandatory.

8.9. Biomarkers

During the study, blood and saliva will be collected for the assessment of biomarkers at the time points indicated in the TES. Additional instructions for collection of biomarker samples:

- Blood biomarkers will be collected under fasting conditions – at least 4 hours, water permitted.
- Subjects should be informed not to do strenuous sports or exercises within 24 hours before blood sample collection.
- Food, drinks (except water) and oral care (brushing, flossing, mouthwash) are not permitted for 1 hour prior to saliva collection.
- Subjects should refrain from alcohol consumption for 12 hours prior to saliva sampling.
- Subjects may receive a reminder via the smartphone to collect the saliva samples on time.

In blood and/or saliva, biomarkers related to the HPA axis activation including but not limited to ACTH and cortisol, neurotropic factors, inflammation and metabolic factors may be investigated.

Biomarkers may be added or deleted based on scientific information or technical innovations under the condition that the total volume of blood collected will not be increased. The biomarker data obtained from this study may also be included in an ongoing cross-study analysis to investigate the relationship between depression severity and phenotypes and biomarkers.

Subject data

To evaluate the biomarker results, the following information needs to be documented on each day of collection of blood samples for biomarker analysis.

- Diet (extremes during the previous week)
- In WOCBP: Follicular phase by documenting first day of last menses.
- Any sickness or allergy in the previous 2 weeks

9. STATISTICAL CONSIDERATIONS

9.1. Sample Size Determination

The sample size for the study is determined based on the assumption of a treatment effect size of 0.45 in the mean change from baseline in MADRS total score between JNJ-67953964 treatment group and placebo. The assumed effect size is based on review of the literature looking at the adjunctive treatment with ALKS 5461, a combination of buprenorphine (partial m-opioid receptor agonist and KOR antagonist) and samidorphan (a potent m-opioid receptor antagonist) in MDD patients with an inadequate response to one or two courses of an antidepressant (Fava 2016 and Enrich 2015).

Using the data from the same studies, an estimate of 11 for standard deviation in the change in MADRS total score from baseline was made. Detection of 0.45 effect size with a power of 90% at an overall 1-sided significance level of 0.20, requires 45 subjects in each treatment group (90 subjects in total).

The choice of alpha and beta (1-power) for this Phase study was made in order to increase sensitivity for detecting a therapeutic signal while also maintaining a modest sample size. Thus, power was set to a high value (power=90%; beta=0.10) but the type 1 error rate was specified at 1-sided alpha=0.20. This choice is supported by a publication by Lindborg et al (Lindborg 2014) in which authors note that type 1 and 2 error levels commonly employed in Phase 3 study designs (simple hypothesis tests with 2-sided alpha=0.05 and beta=0.2) are suboptimal for early phase studies and that switching these values (increasing alpha while decreasing beta) can increase Phase 2 productivity and reduce the risk of rejecting a compound with significant therapeutic potential.

When adjusted for a drop-out rate of approximately 5% of subjects during the treatment period, the required number of subjects to be randomized is 96. To achieve this, the estimated number of subjects to enter the lead in period is 142, after adjusting for an estimated placebo response rate of 25% and drop-out rate of 10% during the lead-in period.

A blinded sample size re-estimation is anticipated with 180 as the maximal number of subjects to be enrolled in the trial.

9.2. Efficacy Analyses

9.2.1. Primary

Primary efficacy analyses will be based on the intention-to-treat analysis set from enriched population (eITT) which consists of randomized lead-in placebo non-responders receiving at least one dose of study medication and having at least one post-treatment baseline efficacy measurement.

The JNJ-67953964 treatment group will be compared with placebo using the primary efficacy endpoint: change from treatment baseline in MADRS score during the treatment period. The comparison will be performed by means of a mixed-effects model for repeated measures

(MMRM), with time, treatment (placebo, JNJ-67953964) and time-by-treatment interaction as factors and baseline total MADRS score as a continuous covariate. Other covariates of interest may be included in the MMRM model. The treatment-placebo differences will be obtained using the appropriate contrast in the MMRM models at the 6-week endpoint.

Sensitivity analyses of the primary endpoint will be performed using an analysis of covariance (ANCOVA) model; these will be detailed further in the Statistical Analysis Plan.

In addition, same MMRM model will be fitted on full intention-to-treat analysis (fITT) set consisting of all the randomized subjects receiving at least one dose of study medication and having at least one post-treatment baseline efficacy measurement.

Missing data mechanisms exploration and possible imputation methods for primary efficacy variable will be described in detail in Statistical Analysis Plan.

Descriptive statistics for actual values and changes from baseline for MADRS Score at each time point of the double-blind treatment phase will be provided by treatment group using both: eITT and fITT analysis sets. Mean differences between the treatments with corresponding confidence intervals (CIs) will be reported.

Frequency tables for response and remission of depressive symptoms (derived from the MADRS) will be provided by treatment group at each time point of the double-blind treatment phase using both: eITT and fITT analysis sets. Chi square test to test the overall differences between the treatment groups will be performed.

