4.2. Scientific Rationale for Study Design

Design aspects, blinding and control

Randomization will be used to minimize bias in the assignment of subjects to treatment groups, to increase the likelihood that known and unknown subject attributes (e.g., demographic and baseline characteristics) are evenly balanced across treatment groups, and to enhance the validity of statistical comparisons across treatment groups.

A placebo control will be used to establish the frequency and magnitude of changes in clinical endpoints, both efficacy and AEs, that may occur in the absence of active treatment. A placebo lead-in period will be used to enrich the population in the treatment phase and minimize the impact of the expectation bias on the part of subjects and investigators on treatment effect. For the same reason, the investigators and subjects will be blinded for the definition of responder/non-responder during the lead-in period.

The primary analysis includes only those subjects who do not have a significant decline during the placebo run-in period ('non-responders to placebo treatment') to increase the sensitivity to a signal of efficacy of JNJ-67953964.

Placebo lead-in responders will also be randomized to active or placebo during the treatment period to expose more subjects to JNJ-67953964 and to obtain the estimate of its effect and safety in a more general population.

Withdrawal placebo period will be used to aid the blinding of the lead-in period duration and exact beginning and ending of the treatment period and will allow exploration of duration of effect and for indication of symptoms of withdrawal from treatment with JNJ-67953964 including re-emergence of symptoms.

Blinding of the lead-in and withdrawal period duration, exact point of randomization and treatment assignment will be used to reduce potential expectation bias from subjects and investigators during evaluation of clinical endpoints as well as AEs.

The double-blind treatment duration is 6 weeks. This is considered an acceptable duration of treatment in a study with antidepressant medication and is supported by available preclinical data (US FDA 1977).

As there will be a placebo withdrawal period after the active treatment period, there will be no separate follow-up period in this study.

Study population

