- Have a MADRS total score of ≥ 25 at screening. If 2 weeks or more elapse between the MADRS rating at screening and Visit 2, the local rater will complete the MADRS again by a telephone interview up to 4 days before Visit 2. At this telephone interview, MADRS total score should again be ≥ 25 and should not demonstrate a clinically significant change (i.e., an improvement of $>20\%$).
- In a common population of subject suffering from MDD, about 90% have a SHAPS total score >20 . The SHAPS total score will initially not be an inclusion criterion. However, after 50 subjects have been randomized, the subjects' properties will be reviewed. If less than 50% of non-responding subjects have a SHAPS total score >20 , then for the remaining subjects the following inclusion criterion will be added:
 - Have a SHAPS total score >20 at screening and baseline (Visit 2)

5. Criterion modified by Amendment INT-3.

5.1. **Men** who are sexually active with a woman of childbearing potential and have not had a vasectomy must agree to use a barrier method of birth control i.e., a condom with spermicidal foam/gel/film/cream/suppository for the duration of the study plus 3 months after receiving the last dose of study drug, and all men must not donate sperm during the study and for 3 months after receiving the last dose of study drug. In addition, their female partners should also use an additional method of birth control (which may include a hormonal method, an intrauterine device [IUD] or an intrauterine system [IUS]) for at least the same duration.

6. Criterion modified by Amendment INT-2

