6.3. Measures to Minimize Bias: Randomization and Blinding

Procedures for Randomization

Central randomization will be implemented in this study. Subjects will be randomly assigned to one of two treatment groups based on the first of two computer-generated randomization schedules prepared before the study by, or under the supervision of the sponsor.

The randomization will be balanced by using randomly permuted blocks stratified by lead-in response status and anhedonia (SHAPS total score <20 vs \geq 20).

Exact timing of randomization for each subject will be blinded. The interactive web response system (IWRS) will assign a unique treatment code, which will dictate the treatment assignment and matching study drug kits for the subject. The requestor must use his or her own user identification and personal identification number each time when contacting the IWRS, and will then give the relevant subject details to uniquely identify the subject.

Blinding

Blinded treatment will be used to reduce potential bias during data collection and evaluation of clinical endpoints.

The investigator will not be provided with randomization codes. The codes will be maintained within the IWRS, which has the functionality to allow the investigator to break the blind for an individual subject.

Data that may potentially unblind the treatment assignment (e.g., study medication plasma concentrations, plasma biomarkers) will be handled with special care to ensure that the integrity of the blind is maintained and the potential for bias is minimized. This can include making special provisions, such as segregating the data in question from view by the investigators, clinical team, or others as appropriate until the time of database lock and unblinding. Also, the site staff should not discuss insights on unblinding of randomization with the subjects.

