9.2.2. Secondary

Evaluation of Anhedonia

Change from treatment baseline in SHAPS score during the treatment period will be analyzed with the same MMRM model as primary efficacy variable (MADRS) using both: eITT and fITT analysis sets. The JNJ-67953964 treatment group will be compared with placebo using the appropriate contrast in the MMRM model at the 6-week endpoint.

Descriptive statistics for actual values and changes from baseline for SHAPS total score at each time point of the double-blind treatment phase will be provided by treatment group using both: eITT and fITT analysis sets. Mean differences between the treatments with corresponding CIs will be reported.

The effect of JNJ-67953964 on depression symptoms across different baseline levels of anhedonia will be explored. Descriptive statistics for actual values and changes from baseline in MADRS Score within different anhedonia levels (no anhedonia, low level of anhedonia and high level of anhedonia; cutoff values will be provided in Statistical Analysis Plan) will be presented by treatment group using both: eITT and fITT analysis set.

Evaluation of Depression

Descriptive statistics for actual values and changes from baseline for CGI-S, SATE and SMDDS (total) scores at each time point of the double-blind treatment phase will be provided by treatment group using both: eITT and fITT analysis sets. In addition, for CGI-S, frequency tables will be provided by treatment and time-point.

Evaluation of Anxiety

Descriptive statistics for actual values and changes from baseline for SIGH-A total score as well as HAM-A₆ score at each time point of the double-blind treatment phase will be provided by treatment group using both: eITT and fITT analysis sets. Mean differences between the treatments with corresponding CIs will be reported.

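### Protocol efficacy MMRM: name baseline SHAPS as covariate for the SHAPS analysis, and the randomisation factors for the MADRS analyses (optional, free improvement)

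*Protocol*

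**What the plan says.** Protocol 9.2.1 compares the arms by an MMRM with "time, treatment (placebo, JNJ-67953964) and time-by-treatment interaction as factors and baseline total MADRS score as a continuous covariate". It then adds: "Other covariates of interest may be included in the MMRM model". That permits further terms but names none.

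The model is used twice more. For the full set, 9.2.1 says the "same MMRM model will be fitted on full intention-to-treat analysis (fITT) set". For anhedonia, 9.2.2 says that change in SHAPS "will be analyzed with the same MMRM model as primary efficacy variable (MADRS) using both: eITT and fITT analysis sets". Neither sentence says whether baseline SHAPS replaces or joins baseline MADRS.

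Protocol 6.3 states: "The randomization will be balanced by using randomly permuted blocks stratified by lead-in response status and anhedonia", with SHAPS cut at 20. Neither factor is named in the model. The primary set (eITT) contains lead-in non-responders only.

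The SAP supplied is the population PK and PK/PD plan. Its section 4.6 tests baseline MADRS or SHAPS as covariates, and lead-in response for full-dataset MADRS. It does not test lead-in response for SHAPS, because blinded data showed no effect on SHAPS during the lead-in.

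**The concern.** The best single predictor of a scale's later score is usually its own baseline. If 9.2.2 is applied as written, the SHAPS model carries baseline MADRS in that place, and the SHAPS comparison gives up precision that data already collected would recover. This matters because SHAPS is a named secondary objective and, apart from MADRS, the only efficacy scale with a model-based comparison in section 9.2.

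In addition, when randomisation is stratified on a prognostic factor and the model omits it, the reported standard error is somewhat too large and the test slightly conservative. In eITT only the SHAPS factor can act this way, since lead-in status is constant there. In the full set both factors vary.

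**Working it through.** **1. The plan's own figure.** Inputs from Protocol 9.1: effect size 0.45, SD 11 (so 4.95 points), one-sided alpha 0.20, power 90%. n per arm = 2(0.8416 + 1.2816)²/0.45² = 44.5, so 45. Then 45/0.95 = 47.4, so 48 per arm and 96 in total; 96/(0.75 × 0.90) = 142. All three reproduce. Power at 45 per arm is 90.2%.

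**2. Primary eITT analysis, SHAPS stratum omitted.** Protocol 5.2 says that in MDD "about 90% have a SHAPS total score >20", so take p = 10% in the low stratum. The stratum gap D in MADRS change is assumed.

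- Share of variance explained = p(1−p)D²/121.
- Overstatement of the reported SE: f = 1/√(1−share).
- Actual alpha = 1 − Φ(0.8416 f).
- SE with the factor = 11 √(1−share) √(2/45). Power with the factor = Φ(4.95/SE − 0.8416); without it, Φ(4.95/SE − 0.8416 f).

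| D (points) | share | f | alpha | power with / without | loss (points) |
|---|---|---|---|---|---|
| 3 | 0.7% | 1.003 | 0.199 | 90.32 / 90.27% | 0.05 |
| 5 | 1.9% | 1.009 | 0.198 | 90.54 / 90.41% | 0.13 |
| 8 | 4.8% | 1.025 | 0.194 | 91.08 / 90.74% | 0.34 |

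Using continuous baseline SHAPS, an assumed partial correlation of 0.1, 0.2 or 0.3 with MADRS change would lift power from 90.2% to 90.4%, 90.9% or 91.9%.

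The low stratum could be larger. Protocol 5.2 adds SHAPS >20 as an entry criterion only if fewer than half of the non-responders among the first 50 randomised exceed 20. With 25% responders, about 37 of those 50 are non-responders, so at least 19 would score 20 or less. Even if no later subject did, 19/96 = 20%. With p = 20% and the same gaps, the SE is overstated by 0.6%, 1.7% or 4.5% and the power loss is 0.09, 0.24 or 0.59 point.

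**3. SHAPS.** The documents give no SHAPS SD, correlation or effect, so all inputs are assumed. Set the baseline SD to 1, the Week 6 SD to k, the baseline-to-Week-6 correlation to ρ and the baseline MADRS-SHAPS correlation to r (0 or 0.3).

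- Variance of change given baseline MADRS: k² + 1 − 2kρ − r²(kρ − 1)².
- Variance given baseline SHAPS: k²(1 − ρ²).
- Reported SE ratio: square root of the first over the second. For k = 1, ρ = 0.4, r = 0: √(1.20/0.84) = 1.195.

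Excess of the reported SE when baseline SHAPS is left out:

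| k | ρ = 0.4 | ρ = 0.6 | ρ = 0.8 |
|---|---|---|---|
| 0.8 | 34-36% | 26-29% | 23-25% |
| 1 | 18-20% | 11-12% | 5% |
| 1.25 | 8-9% | 3% | 0% |
| 1.5 | 4% | 0% | 2% |

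Simulating a Week 6 ANCOVA with k = 1 and 45 per arm under stratified randomisation gave a true SE 13-15%, 7-9% and 4% larger at ρ = 0.4, 0.6 and 0.8. This is less than the reported excess, because stratification already balances part of baseline SHAPS. Rejection under the null was 0.184-0.199 with baseline MADRS and 0.195-0.208 with baseline SHAPS, against a nominal 0.20. A generalised least squares check of a five-visit unstructured MMRM with equal SDs kept most of the gain.

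**4. MADRS in the full set.** About 142 × 0.9 × 0.95 = 121 subjects, p = 25% responders. Section 4.2 says the primary analysis includes "only those subjects who do not have a significant decline during the placebo run-in period", so responders should start treatment with lower MADRS, and baseline MADRS may already carry part of their difference. Assumed: responders g = 8 to 15 points lower at treatment baseline, within-stratum baseline SD s = 5, slope b = −0.2 to −0.6. D is responder minus non-responder mean change (positive = less improvement) and w² the within-stratum variance of change.

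- Residual variance without lead-in status: Vy − Cxy²/Vx, where Vx = s² + p(1−p)g², Cxy = bs² − p(1−p)gD, Vy = w² + p(1−p)D².
- With it: w² − b²s².

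Three cases:

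- g = 10, b = −0.4, D = +4, w² = 121: Vx = 43.75, Cxy = −17.5, Vy = 124. Without: 124 − 7 = 117. With: 117. Ratio 1.00.
- g = 8, b = −0.2, D = +8, w² = 121 − 12 = 109: Vx = 37, Cxy = −17, Vy = 121. Without: 113.2. With: 108. SE ratio 1.024.
- g = 10, b = −0.6, D = −8, w² = 109: Cxy = 0. Without: 121. With: 100. SE ratio 1.10.

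Over the whole grid, the SE is about 0-2% larger if responders later improve 4-8 points less than non-responders, and about 1-10% larger if they improve 4-8 points more. In seven simulated scenarios, rejection under the null without the factor was 0.178-0.205.

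**The case against.** The strongest objection is that the clinical SAP is not among the documents. Protocol 9.2 sends the ANCOVA sensitivity analyses, missing-data methods and anhedonia cut-offs to a Statistical Analysis Plan, and that is where covariates would normally be fixed. 9.2.1 leaves room for them. This stands: the point concerns the protocol wording only and does not show that the terms are absent from the full plan.

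Second, reusing the model for SHAPS may simply mean the same structure with the outcome's own baseline. That is a natural reading. The protocol does not say which is meant, and one clause would settle it.

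Third, the SHAPS gain is not assured. It depends on the ratio of the Week 6 to the baseline SD as well as on the correlation, and it can nearly vanish. This also stands. It is the reason for giving a range from about zero upward, and for giving no SHAPS power figure, since the protocol sets neither power nor alpha for that endpoint.

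Two stronger readings are tempting, and the documents do not support them. A reader might infer that leaving out stratification factors undermines the primary test. It does not: lead-in status is constant in eITT, the SHAPS stratum changes power by a fraction of a point, and the error in alpha is on the conservative side. A reader might also infer that adding the SHAPS >20 entry criterion would almost empty the low stratum. Its trigger in 5.2 implies the opposite, a low stratum of about 20% or more.

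**Conclusion.** The point holds as an optional, free improvement to protocol wording. There is no bias and no excess of false positives.

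The likeliest gain is in the SHAPS analysis, if baseline SHAPS really is left out. The reported SE is then about 5-20% larger with equal SDs, about 0-9% larger if the Week 6 SD is 1.25 to 1.5 times baseline, and about 23-36% larger if it is 0.8 times baseline, for correlations of 0.4 to 0.8. In the primary analysis the effect is negligible: 0.05 to 0.34 point of power with a 10% low stratum, and about 0.1 to 0.6 point at 20%. For MADRS in the full set the range is about 0-10% of the SE. Its size depends on an unknown responder difference, so no single figure is claimed. Every stratum gap, correlation and SHAPS variance here is an assumption; only the design figures of 9.1 and the approximate 90% SHAPS share come from the protocol.

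**What to change.** In Protocol 9.2.2, state that the SHAPS MMRMs use treatment-baseline SHAPS as the baseline covariate. In 9.2.1, include lead-in response status in the full-set MADRS MMRM, and baseline SHAPS (continuous, or its stratum) in the MADRS MMRMs. Lead-in status cannot be estimated in eITT. It is not needed for SHAPS, given the blinded finding reported in SAP 4.6. The exploratory PK/PD model needs no change.

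If the clinical SAP already says this, a cross-reference is enough. Otherwise the cost is one or two sentences before unblinding and 1-2 degrees of freedom. SHAPS is already scheduled at every visit and lead-in status is already used for randomisation, so no new data or subjects are needed.

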## 2. OBJECTIVES

The primary objectives of the population pharmacokinetic (PK) and pharmacodynamic (PD) analysis are as follows:

- To characterize the pharmacokinetics of 10 mg qd JNJ-67953964 after oral administration, including
  - an exploratory analysis to determine if any relevant covariate could explain the variability in exposure of JNJ-67953964;
  - derivation of individual exposure parameters for JNJ-67953964 (i.e. area under the plasma concentration-time profile of JNJ-67953964 over 24 hours, AUC0-24h maximum plasma concentration, Cmax, and pre-dose plasma concentrations, C0h). Exposure metrics will be derived from the popPK model on the study days with MADRS and SHAPS assessments;
- To explore the relationship of JNJ-67953964 exposure with efficacy using the change from baseline in Montgomery-Asberg Depression Scale (MADRS) total score and change from baseline in Snaith-Hamilton Pleasure Scale (SHAPS);
- To explore potential relationship between JNJ-67953964 exposure and pre-defined safety parameters. AEs of special interest may include pruritus and gastrointestinal (GI) complaints.

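### Response and remission are compared with an unadjusted chi-square test; in fITT this is valid but can be conservative and lose up to about 5 points of power if lead-in strata differ strongly

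*Protocol*

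**What the plan says.** Protocol section 9.2.1 describes the binary endpoints in two sentences, which the synopsis repeats. "Frequency tables for response and remission of depressive symptoms (derived from the MADRS) will be provided by treatment group at each time point", in both eITT and fITT; then "Chi square test to test the overall differences between the treatment groups will be performed". No stratum, covariate or effect estimate with CI is attached to this comparison, and response and remission are not defined.

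The surrounding text shows what was available:

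- Section 6.3 randomises by "randomly permuted blocks stratified by lead-in response status and anhedonia", with SHAPS split at 20.
- The primary MMRM uses "baseline total MADRS score as a continuous covariate". The permission to adjust further is confined to that model: "Other covariates of interest may be included in the MMRM model".
- eITT is restricted to "randomized lead-in placebo non-responders receiving at least one dose of study medication" who also have a post-baseline efficacy measurement. fITT applies the same dose and measurement conditions to all randomised subjects, so it includes lead-in responders.
- On missing data: "Missing data mechanisms exploration and possible imputation methods for primary efficacy variable will be described in detail in Statistical Analysis Plan". Nothing is said about missing scores for response or remission.

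The supplied SAP does not fill these gaps. Its scope is set by its section 2: "The primary objectives of the population pharmacokinetic (PK) and pharmacodynamic (PD) analysis are as follows". The clinical SAP to which the protocol refers is not among the documents.

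**The concern.** Stratified randomisation balances the arms on lead-in response and SHAPS, so the variation between strata does not contribute to the error of the treatment comparison. A pooled chi-square still counts that variation in its standard error. If a stratification factor predicts outcome strongly, the standard error is too large, the true type I error falls below nominal, and power is lost.

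The set at risk is fITT. It mixes two groups that the protocol separates because it expects them to differ in their sensitivity to a drug signal (section 4.2). What is at stake is some efficiency in a supportive comparison, not the primary MADRS result.

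**Working it through.** **1. The plan's own figures.** Per arm, n = 2(z0.80 + z0.90)²/d² = 2(0.8416 + 1.2816)²/0.45² = 44.5, so 45. With 5% dropout, 45/0.95 = 47.4, so 48 per arm and 96 in all. Entering lead-in: 96/(0.75 × 0.90) = 142.2. All match Protocol section 9.1. Lead-in responders also randomised: 142 × 0.90 × 0.25 = 31.95, about 32. fITT is therefore taken as 48 lead-in non-responders plus 16 responders per arm, and eITT as 48 per arm.

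**2. Why pooling is conservative in fITT.** Let R be the mean within-stratum variance divided by the pooled variance p(1 − p), with stratum weights 0.75 and 0.25. At nominal one-sided 0.20, type I error is about 1 − Φ(0.8416/√R). For assumed placebo response of 20% in non-responders and 80% in responders:

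- pooled p = 0.75 × 0.20 + 0.25 × 0.80 = 0.35, variance 0.35 × 0.65 = 0.2275
- within-stratum variance = 0.16
- R = 0.16/0.2275 = 0.703, √R = 0.839
- type I error ≈ 1 − Φ(1.003) = 0.158

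Simulation (200,000 trials) gives 0.159 for chi-square and 0.206 for Cochran-Mantel-Haenszel (CMH).

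**3. Power in fITT**, treatment log-odds 0.5, one-sided 0.20, 200,000 trials per row:

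| Assumed placebo response (non-responders / responders) | R | Approx. type I error, chi-square | Power, chi-square | Power, CMH |
|---|---|---|---|---|
| 20% / 80% | 0.703 | 0.158 | 58.5% | 63.2% |
| 25% / 70% | 0.836 | 0.179 | 65.3% | 65.8% |
| 30% / 70% | 0.875 | 0.184 | 68.1% | 68.2% |
| 25% / 50% | 0.945 | 0.193 | 68.2% | 68.2% |

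The approximation ignores discreteness. Simulated type I error (20,000 trials) was 0.183 at 25%/70% and 0.186 at 25%/50%. With odds ratio 2 instead, power for chi-square and CMH was 81.9% and 82.2% at 25%/70%, and 84.7% for both at 25%/50%.

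**4. eITT.** Lead-in status is constant, so only SHAPS remains. Section 5.2 expects about 90% of subjects above 20, giving strata of about 86 and 10. With control rates of 25% and 35%, type I error is 0.204 for chi-square and 0.203 for CMH. Power is 63.5% and 63.2% at log-odds 0.5, and 79.0% and 78.6% at odds ratio 2. An even SHAPS split with rates of 20% and 35% gives 78.3% and 78.4%. Stratifying gains essentially nothing.

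**5. Baseline MADRS** (logistic regression, 48 per arm, odds ratio 2, 3,000 trials). Power moves from 77.4% to 76.6% if baseline shifts the log-odds by 0.3 per SD, and from 74.2% to 76.1% if it shifts them by 0.7 per SD.

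**6. Missing scores, if an observed-case denominator were used.** Suppose 30% of all randomised subjects respond in each arm, every dropout is a non-responder, and dropout is 15% against 5%. The observed-case difference is 0.30/0.85 − 0.30/0.95 = 0.353 − 0.316 = 0.037, a spurious 3.7 points in favour of the arm with more dropout. With equal dropout it is zero. Section 9.1 plans for about 5% dropout overall and gives no figure by arm.

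**The case against.** The strongest reply is that a chi-square test is acceptable for a supportive endpoint, that its error here is in the safe direction, and that the clinical SAP may already refine it. Much of this stands. Pooling does not inflate type I error. In eITT, the primary set, the choice makes no practical difference. A loss near 5 points needs a 60-point gap between lead-in strata, and nothing in the documents supports so wide a gap. If response is measured from treatment baseline, lead-in responders start from an already reduced score and need not respond at 80%. What remains is that the protocol names an unadjusted test for fITT when better-matched methods are available at almost no cost.

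Three stronger readings are tempting and are not supported:

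- *The test drops subjects without a score.* A reader might infer this from tables given by time point, and might add that section 7.3 withdraws subjects who worsen. The protocol sets no denominator rule. Missing scores could equally be counted as non-response, carried forward or shown as a separate row. The SAP's rule against imputing MADRS belongs to the PK/PD analysis and does not govern these tables.
- *The test contradicts the trial's one-sided design.* The one-sided 0.20 in section 9.1 sizes the comparison of mean MADRS change. Nothing obliges a supportive binary comparison to share it, so sidedness is a preference.
- *The primary conclusion is affected.* The primary analysis is the MMRM in eITT, which does not use this test.

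**Conclusion.** The point holds in a limited form and is minor. The unadjusted chi-square in section 9.2.1 is valid in both sets. In fITT it can be conservative and give up between about 0 and 5 points of power, with a material loss only if response differs strongly between lead-in responders and non-responders. In eITT there is essentially no gain from stratifying by SHAPS. Adjusting for baseline MADRS changed power by −0.8 to +2.0 points at the two prognostic strengths in step 5.

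These sizes rest on assumed response rates, treatment effects and prognostic strengths, because the documents give none for response or remission, and on the planned numbers without further loss. The handling of missing scores is unspecified, not wrong: an observed-case denominator would be biased if non-responders dropped out more in one arm, but the protocol does not prescribe one.

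**What to change.** In the clinical SAP, for response and remission at treatment Week 6:

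- In fITT, replace the chi-square with a CMH test stratified by lead-in response, adding SHAPS where cell sizes allow. With about 10% of subjects expected at or below 20, the low-SHAPS cell among lead-in responders would hold only about 0.10 × 32 = 3 subjects.
- Alternatively, in both sets, use logistic regression with treatment-baseline MADRS and the randomisation strata. In eITT the only stratum left is SHAPS.
- Report a risk difference with CI: stratum-weighted with CMH, or standardised from the logistic model.
- Define response and remission, including the baseline used, and state how a subject without a score at the visit is counted, for example as non-response.

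The cost is SAP wording before unblinding, with no new data or subjects. Counting missing scores as non-response slightly lowers the quoted rates: with 5% dropout, a 25% rate among completers becomes 0.25 × 0.95 = 23.75%.
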